Continuous Glucose Monitoring in Hospitalized Patients With Diabetes Mellitus

NCT#04653454

12August2020

IRB Minimal Risk Protocol Template

Note: If this study establishes a human specimen repository (biobank) for research purposes, do not use this template. Use the Mayo Clinic Human Specimen Repository Protocol Template found on the IRB home page under Forms and Procedures at

[REDACTED]

First-time Use: Use this template to describe your study for a new IRB submission.

1. Complete the questions that apply to your study.
2. Save an electronic copy of this protocol for future revisions.
3. When completing your IRBe application, you will be asked to upload this document to the protocol section.

Modification: To modify this document after your study has been approved:

1. Open your study in IRBe. Click on the study 'Documents' tab and select the most recent version of the protocol. Save it to your files.
2. Open the saved document and activate "Track Changes".
3. Revise the protocol template to reflect the modification points, save the template to your files
4. Create an IRBe Modification for the study and upload the revised protocol template.

General Study Information

Principal Investigator: [name].

Study Title: CGM use in hospitalized patients with diabetes mellitus.

Protocol version number and date: Version 1.0, 8/12/2020

Research Question and Aims

Hypothesis: Patient's own CGM (continuous glucose monitor) used in the hospital will be as accurate as POC (point of care) glucose monitors and acknowledgement by providers of high and low glucose trends will prevent episodes of hyper and hypoglycemia.

Aims, purpose, or objectives:

1. To determine if patient's own CGMs worn in the non-ICU hospital setting have adequate accuracy for blood glucose monitoring when compared to point-of-care capillary glucose measurement.
2. To determine if alerts given by CGMs worn in the non-ICU hospital would prevent episodes of hyperglycemia and hypoglycemia.

Background (*Include relevant experience, gaps in current knowledge, preliminary data, etc.*):

Diabetes Mellitus (DM) affects approximately 34.2 million (10.5%) Americans. Hyperglycemia and hypoglycemia in hospitalized patients have been associated with unfavorable clinical outcomes, including higher rates of sepsis, deconditioning, mortality and longer hospital stay. Untreated

hypoglycemia may lead to neurological damage, cognitive decline, seizures and coma. Additionally, the management of the diabetic complications doubles the inpatient cost per capita compared to non-diabetic patients.

Current standard of care in the hospital recommended by the national guidelines is the bedside point-of-care (POC) glucose capillary testing performed before meals and at bedtime. This approach however does not provide continuous 24-h glucose measurement and fails to detect nocturnal or asymptomatic hypoglycemia or hyperglycemia, all of which are common insulin therapy complications.

Continuous Glucose Monitoring (CGM) represents an alternative with the potential to assist making personalized therapy decisions. It measures levels of interstitial glucose every 5-15 min, which provides better assessment of nocturnal or asymptomatic hypoglycemia or hyperglycemia and shows glycemic patterns following treatment interventions. The ability to monitor glucose more frequently will also allow for timely interventions, and thus hyperglycemia and hypoglycemia episodes can be reduced. There have been studies demonstrating improved glycemic control in insulin-treated DM patients using CGM in outpatient setting, and even a few studies describing the use of CGM in non-ICU hospitalized patients.

Prospective studies evaluating the use of the newer CGMs in non-critically ill hospitalized patients are lacking. The aim of our study therefore was to compare the accuracy of patient's own CGM monitor worn in the hospital in detecting blood glucose levels by comparing them with those measured by a POC blood glucose capillary test.

Study Design and Methods

Methods: *Describe in lay terms, completely detailing the research activities that will be conducted by Mayo Clinic staff under this protocol.*

All patients admitted to the hospital in inpatient or observation status and having a CGM monitor attached will be screened and identified by providers and nurses. An order will be placed by providers to continue patient's home CGM monitor use in the hospital. A CGM patient agreement describing the hospital policy for use of CGMs will be provided to the patient for signature. (see attached agreement) Patients will be encouraged to continue to wear their CGMs in the hospital unless their presence interferes with patients' medical care. CGM presence will be recorded by nursing in patient chart under LDA (lines, drains, airway) section. A daily report will be run and these patients identified. Patients will be approached by research staff and asked to be enrolled in the study. A research consent will be reviewed with the patients and will be provided to patients for signature. Patients will be asked to continue to use their home CGMs in the hospital. If the sensor will reach the end of life patients have the option to place a new sensor and follow manufacturer recommendations for calibration and setting. Patients are responsible to provide their own sensors, transmitters, readers during the hospitalization period. If it is determined that the current sensor will interfere with the in-hospital medical and surgical care (MRI testing, procedure at the site, etc.), patient will be asked by their providers to remove the sensor and transmitter. Patients will have the option to replace the sensor after the procedure if they so desire. Patients will continue to monitor their glucose via CGM and their approved devices. For flash sensors, patients will be asked to scan their sensor at least every 8 and as needed. CGMs that require calibration will be calibrated by patients using hospital POC glucose meter readings. .

Patients alerted by their CGM about low glucose levels or fast downward or upward trending will be asked to notify their nursing staff. A POC blood glucose check will be done by nursing staff to confirm the alert or the trend. Treatment decisions will be made based on POC readings.

During hospitalization patients will continue to have their blood glucose checked with POC glucose monitor per hospital policy.

Treatment of the DM and associated complications, dosing of the insulin, change from PO to insulin treatment and back to PO medications during hospitalization or at discharge will be guided by the admitting team with as needed help from the inpatient Endocrinology Consultation Service.

Decisions about insulin dosing or other medication use designed to treat hyper or hypoglycemia episodes or underlying diabetes mellitus will be made based on hospital POC blood glucose meters and not based on CGM readings alone.

Patients will be asked to give the research team “provider access” to their cloud CGM software, or to allow the team to download their CGM data prior to discharge if their reading devices do not automatically synchronize with the cloud software.

CGM data will be compared with POC blood glucose monitoring obtained in the hospital. Different patient variables (demographics, comorbidities, labs and vitals, administered medications) will be collected from electronic health record and will be evaluated to determine if they would interfere with CGM readings. The accuracy of CGM for glucose measurement in the hospital will be calculated.

Outcomes measured:

CGM accuracy when compared with POC monitors.

CGM accuracy at detection of hypo or hyperglycemia episodes when compared with POC monitors.

Number of CGM alarms and the clinical result of these alarms: nurse notification, treatment of hypo or hyperglycemia episodes, treatment for rapid declining glucose alarms.

Materials:

CGMs (sensors, transmitters and readers) belong to patients

Provider access to cloud CGM program will be granted to the research team by the patient.

Personnel:

A research assistant that will identify the patients and enroll them into the study.

Subject Information

Target accrual is the proposed total number of subjects to be included in this study at Mayo Clinic. A “Subject” may include medical records, images, or specimens generated at Mayo Clinic and/or received from external sources.

Target accrual: 150

Subject population (children, adults, groups): Admitted adult medical and surgical patients with Diabetes Mellitus type I or II that have their own CGM monitor present on admission or able to be placed after admission.

Inclusion Criteria:

Patients with Type 1 or 2 Diabetes Mellitus,

Patients 18 years of age or older,

Patients admitted under medical or surgical services.

Patients treated with diet alone, insulin (SQ, insulin pump) or oral hypoglycemic medications.

Exclusion Criteria:

COVID-19 infection,

Infection of the skin at the CGM site requiring removal of the sensor.

Patients with altered Mental Status,

Patients unable to scan their flash CGMs at least every 8 hours.

Inability to provide written consent.

Hospitalized for less than 24h

Biospecimens

Collection of blood samples. When multiple groups are involved copy and paste the appropriate section below for example repeat section b when drawing blood from children and adults with cancer.

a. **From healthy, non-pregnant, adult subjects who weigh at least 110 pounds.** For a minimal risk application, the amount of blood drawn from these subjects may not exceed 550ml in an 8 week period and collection may not occur more frequently than 2 times per week.

Volume per blood draw: _____ ml

Frequency of blood draw (e.g. single draw, time(s) per week, per year, etc.) _____

b. **From other adults and children considering age, weight, and health of subject.** For a minimal risk application, the amount of blood drawn from these subjects may not exceed the lesser of 50 ml or 3 ml per kg in an 8 week period, and collection may not occur more frequently than 2 times per week.

Volume per blood draw: _____ ml

Frequency of blood draw (e.g. single draw, time(s) per week, per year, etc.) _____

Prospective collection of biological specimens other than blood: _____

Review of medical records, images, specimens

Check all that apply (data includes medical records, images, specimens).

Only data that exists before the IRB submission date will be collected.

Date Range for Specimens and/or Review of Medical Records:

Examples: *01/01/1999 through 12/31/2015*, or all records through *mm/dd/yyyy*.
01/01/2010 through 01/01/2022

Note: The Date Range must include the period for collection of baseline data, as well as follow-up data, if applicable.

The study involves data that exist at the time of IRB submission **and** data that will be generated after IRB submission. Include this activity in the Methods section.

Examples

- The study plans to conduct a retrospective chart review and ask subjects to complete a questionnaire.
- The study plans to include subjects previously diagnosed with a specific disease and add newly diagnosed subjects in the future.

The study will use data that have been collected under another IRB protocol. Include in the Methods section and enter the IRB number from which the research material will be obtained. *When appropriate, note when subjects have provided consent for future use of their data and/or specimens as described in this protocol.*

Enter one IRB number per line, add more lines as needed

Data Specimens Data & Specimens _____

Data Specimens Data & Specimens _____

Data Specimens Data & Specimens _____

Data Analysis

Power analyses may not be appropriate if this is a feasibility or pilot study, but end-point analysis plans are always appropriate even if only exploratory. Provide all information requested below, or provide justification if not including all of the information.

Power Statement:

Data Analysis Plan:

Data will be described as percentages or means. Pearson χ^2 and Kruskal Wallis tests will be used to compare categorical and continuous variables respectively. Odds ratios, 95% confidence intervals and p-values will be reported for each model. All tests of significance will be 2-sided and the level of statistical significance will be set at p-value < 0.05.

Mean Absolute Relative Differences will be calculated between matched pairs of POC monitors and the closest CGM reading (within 5 minutes of POC). Additionally, level of agreement between the two devices will be examined with Bland-Altman plots, with particular attention focused on detection agreement in range (70-180 g/dl). Poisson or negative binomial regression will be utilized to assess count variables such as number of alarms, nurse notification, and hypo or hyperglycemia events adjusting for patient characteristics. Finally, longitudinal analysis will be conducted to determine differences associated with medications, clinical parameters or diagnosis. Analysis will seek to define if there are any differences between CGM and POC measurement based on these changes.

Endpoints

Primary: CGM accuracy - mean absolute relative difference (MARD)

Secondary:

- CGM accuracy at detection of hypo or hyperglycemia episodes when compared with POC monitors. (MARD for readings <70g/dl, >180g/dl, >250g/dl)
- CGM accuracy for detecting time in range (70-180 g/dl MARD).
- Number of CGM alarms and the clinical result of these alarms: nurse notification, treatment of hypo or hyperglycemia episodes, treatment for rapid declining glucose alarms.
- Time in therapeutic range for glucose as measured by CGM and POC glucose monitor.
- Detection of medications, clinical parameters or diagnoses that would interfere with CGM reading.
- Effect of CGM use on length of hospital stay, post-surgical duration of hospitalization

Clinical safety measures:

- Number of sensors with failure.
- Number of sensors removed for procedure.
- Number of sensor related skin reaction (contact dermatitis, infection)

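### Sensors newly placed in hospital are analysed with established home sensors and time since insertion is not modelled, so any early-wear error could be credited to drugs or clinical parameters.

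*Combined protocol and SAP*

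**What the plan says.** The combined protocol and SAP gives three routes to a sensor started in hospital.

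- **End of life** (Study Design and Methods): "If the sensor will reach the end of life patients have the option to place a new sensor". The manufacturer's instructions then govern how it is set up.
- **After removal for MRI or a procedure** (same section): "Patients will have the option to replace the sensor after the procedure if they so desire".
- **First placement after admission** (Subject Information, subject population): eligible patients "have their own CGM monitor present on admission or able to be placed after admission".

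Other patients keep the sensor they wore from home.

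The Data Analysis Plan treats all readings alike: "Mean Absolute Relative Differences will be calculated between matched pairs of POC monitors and the closest CGM reading (within 5 minutes of POC"). It names no stratum, exclusion or sensitivity analysis for newly inserted sensors.

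For interference, the Methods list what is to be taken from the health record: "Different patient variables (demographics, comorbidities, labs and vitals, administered medications"). The Data Analysis Plan then says that "longitudinal analysis will be conducted to determine differences associated with medications, clinical parameters or diagnosis". Detecting interfering medications, clinical parameters or diagnoses is a secondary endpoint. Sensor age, insertion time and replacement status appear in none of these places. The clinical safety measures count failed sensors and sensors removed for a procedure, but neither count gives sensor age or enters a model.

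**The concern.** A longitudinal analysis of CGM-minus-POC differences asks what else changed when agreement changed. When a sensor is removed for a procedure and replaced, a new sensor starts close in time to peri-procedural drugs and to shifts in labs and vitals. If the model has terms for the drugs and clinical parameters but none for the sensor, any difference between a fresh and an established sensor is credited to the terms that are there.

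What is at stake is the secondary interference endpoint. A drug or laboratory value could be reported as disturbing CGM readings when the real cause is that the sensor was new. Enrolling more patients would not remove the bias; it would only make the wrong answer look more precise.

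**Working it through.** The plan has no figure to reproduce here. It gives no early-wear error, replacement rate, effect size or standard deviation. What follows is an illustration of an omitted covariate.

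**Inputs from the documents.** Target accrual 150 (Subject Information); two-sided 0.05 level (Data Analysis Plan).

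**Assumed inputs.**
- d, the extra absolute relative difference (ARD) of a new sensor: 0 to 6 percentage points.
- p1 and p0, the shares of exposed and unexposed patients whose readings come from a new sensor: p1 = 20% to 80%, p0 = 5%.
- 30 of the 150 patients exposed to the drug or clinical factor.
- SD of patient-mean ARD: 5 to 8 points.
- True effect of the factor: zero.

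**Step 1: spurious effect.** Bias = d × (p1 − p0). For d = 4 and p1 = 50%: 4 × 0.45 = 1.8 points.

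**Step 2: false-positive rate.** SE = SD × √(1/120 + 1/30). With SD = 6, SE = 1.22 and 1.8/1.22 = 1.47. The chance of p < 0.05 is Φ(1.47 − 1.96) + Φ(−1.47 − 1.96) = 31%.

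Spurious effect in points, with the false-positive rate at SD 6:

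| d | p1 = 20% | p1 = 50% | p1 = 80% |
|---|---|---|---|
| 0 | 0 (5%) | 0 (5%) | 0 (5%) |
| 2 | 0.3 (6%) | 0.9 (11%) | 1.5 (23%) |
| 4 | 0.6 (8%) | 1.8 (31%) | 3.0 (69%) |
| 6 | 0.9 (11%) | 2.7 (60%) | 4.5 (96%) |

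At the top corner (d = 6, p1 = 80%) the rate is 99% with SD 5 and 79% with SD 8. If p1 = p0, the bias is zero for any d.

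**Step 3: does a sensor term help?** A simulation (2,000 runs per scenario, SD 6, p0 = 5%) fitted least squares with and without a new-sensor term.

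| d, p1 | Bias without term | False positives without term | Bias with term | False positives with term |
|---|---|---|---|---|
| 4, 20% | 0.59 | 8% | −0.02 | 5.0% |
| 4, 50% | 1.75 | 29% | −0.05 | 5.4% |
| 4, 80% | 3.04 | 68% | 0.05 | 5.5% |
| 6, 50% | 2.79 | 58% | 0.09 | 4.9% |
| 2, 50% | 0.92 | 12% | 0.00 | 4.2% |

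**Step 4: price of the term.** For a given residual SD, the SE of the factor's effect grows by 1/√(1 − r²). Here r² = 0.16 × (p1 − p0)² / [m(1 − m)] and m = 0.2 × p1 + 0.8 × p0.
- p1 = 20%: m = 0.08, r² = 0.0036/0.0736 = 0.049, SE × 1.03.
- p1 = 50%: m = 0.14, r² = 0.0324/0.1204 = 0.269, SE × 1.17.
- p1 = 80%: m = 0.20, r² = 0.09/0.16 = 0.563, SE × 1.51.

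**Step 5: pooled MARD.** Shift relative to all-established sensors = d × (30 × p1 + 120 × p0)/150. The largest value is 6 × (24 + 6)/150 = 1.2 points, and the smallest is 0.

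These steps use one mean per patient, not the unspecified longitudinal model, so the false-positive rates are indicative only.

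**The case against.** The strongest reply is that nothing in the documents says a new sensor reads less accurately. That stands: d is an assumption and may be zero. The protocol also has patients follow manufacturer instructions when starting a new sensor. CGMs that need calibration are calibrated with the hospital POC meter, which is also the comparator, so a sensor started in hospital might even agree better with POC at first. This leaves size and direction open, but it does not put sensor age into the analysis.

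The size in the working is also generous. It applies the penalty to every reading of a patient on a new sensor. If only the first 24 hours are affected, p1 should be the share of readings in that window. For a sensor placed at admission and evenly spaced POC checks, that is 24/48 = 50% in a 2-day stay and 24/96 = 25% in a 4-day stay. The upper end of the table therefore needs nearly all exposed readings to fall in early wear.

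A reader might infer four stronger things, none of which the documents support.

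- **That replacement often follows a procedure.** No frequency is given. Removal is limited to interference with care, replacement is optional, and patients supply their own sensors.
- **That the plan tests for a procedure effect.** No before-and-after-procedure contrast is planned. The named factors are medications, clinical parameters and diagnoses.
- **That sensor age and exposure cannot be separated.** Within one patient they may coincide. Across patients, end-of-life replacements, sensors placed after admission and sensors kept on need not coincide with new drugs, so adjustment is possible.
- **That the pooled primary MARD is biased.** Aim 1 concerns patients' own CGMs as worn in hospital, and replacement is part of that use. Dependence on the mix of sensors is case mix.

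**Conclusion.** The concern holds as an omitted covariate in the secondary interference analysis. New and established sensors are analysed together, and time since insertion is neither listed for collection nor modelled. If there is early-wear error, and new sensors coincide with drugs or changed clinical parameters, the plan as written would attribute that error to those factors.

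Both conditions are assumptions. Over the assumed ranges the spurious effect is 0 to about 4.5 points of ARD, and it is zero if either condition fails. The figures illustrate sensitivity and are not estimates for this study. The primary MARD still answers Aim 1 as an as-worn figure; showing how far it depends on new sensors would be a useful addition, not a correction.

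**What to change.** Record each sensor's start date and time, from the CGM download or by asking at enrolment, and any in-hospital replacement with its reason. Insertion times may be hard to recover later, so capture them during enrolment.

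In the longitudinal interference model, add time since insertion as a time-varying term (for example, first 24 hours versus later), with sensor nested in patient. Judge drug and clinical-parameter effects after that adjustment.

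Keep the pooled as-worn MARD as the primary result. As a sensitivity analysis, report it again without pairs from the first 24 hours of any new sensor.

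The cost is one or two data fields, fewer pairs in the sensitivity analysis, and wider intervals for drug and clinical-parameter effects: about 3% to 51% wider under the assumed overlaps in step 4, and most where new sensors and exposure coincide most. Patient care does not change.

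### For calibrated CGMs, the same hospital POC value can both set the device and score it, and the pairing rule does not bar this; the size is undeterminable and may be zero

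*Combined protocol and SAP*

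**What the plan says.** Under Study Design and Methods (Methods), "CGMs that require calibration will be calibrated by patients using hospital POC glucose meter readings". The same hospital meter is the comparator for the whole study.

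The Data Analysis Plan states the pairing rule: "Mean Absolute Relative Differences will be calculated between matched pairs of POC monitors and the closest CGM reading (within 5 minutes of POC". It adds that "level of agreement between the two devices will be examined with Bland-Altman plots". The primary endpoint is "CGM accuracy - mean absolute relative difference (MARD", and a secondary endpoint applies the measure by range ("MARD for readings <70g/dl, >180g/dl, >250g/dl").

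Three further facts set the timing. The Background says of CGM that "It measures levels of interstitial glucose every 5-15 min". It describes standard care as "glucose capillary testing performed before meals and at bedtime", which is about four checks a day if there are three meals. After a CGM alert, "A POC blood glucose check will be done by nursing staff to confirm the alert or the trend", so alert checks can also become pairs or calibration values.

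The pairing rule gives no direction, before or after. The text supplied does not flag POC values entered as calibrations, record entry times, treat such pairs separately or plan an analysis by calibration status. The patient agreement mentioned in the Methods as attached is not available here, so whether it covers recording of calibrations is unknown.

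**The concern.** Suppose a POC value is measured and the patient enters it into the CGM. If the closest CGM reading came before the entry, the pair is a sound comparison. If it came after, the CGM has been moved towards the number it is then scored against, including that number's own meter error. The two sides of the pair share an error, and their difference is too small.

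Part of the closer agreement after an entry is real, because a calibrated sensor reads better. Only the part due to sharing one POC value is artefact, and this point claims only that part.

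The artefact can touch the primary MARD, the range-specific MARDs and the Bland-Altman limits. It favours the hypothesis in Research Question and Aims that the patient's CGM is as accurate as POC. A pooled figure can hide it, because it arises only in devices that are calibrated.

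**Working it through.** The documents state no expected MARD and no size for this effect, so there is no figure of the plan's to reproduce. The check is an illustration.

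**Inputs from the documents:** reading interval g of 5 to 15 minutes; a 5-minute window; about 4 routine POC checks a day.

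**Assumed inputs:** share of pairs from calibrated devices s = 0.25 (the same share of patients, with equal checks each); share of their checks entered as calibrations f = 2/4 = 0.5; meter error SD 5%; sensor noise SD 9%; sensor gain SD 12% (log scale); correlation of sensor noise before and after entry ρ = 0.7; the device moves a fraction k = 0.5 to 1 of the way to the entered value; entry delay d.

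**Step 1: how often the closest reading follows the entry.** With aligned clocks and reading times unrelated to POC times, let h = min(g/2, 5). Then q = max(0, (h − d)/(2h)).

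| Delay d (min) | q, 5-minute readings | q, 15-minute readings |
|---|---|---|
| 0 | 0.50 | 0.50 |
| 1 | 0.30 | 0.40 |
| 2 | 0.10 | 0.30 |
| 2.5 | 0 | 0.25 |
| 5 | 0 | 0 |

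So at most half of calibration pairs are affected when clocks agree. A clock offset moves q either way: with 5-minute readings, a CGM clock 2 minutes slow gives q = 0.4 at a 2.5-minute delay, and one 2 minutes fast gives q = 0.1 at no delay.

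**Step 2: artefact per affected pair.** This is the post-entry MARD against an independent POC value minus the post-entry MARD against the entered value. Simulation gives:

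| k | Before entry | After, same POC | After, independent POC | Artefact |
|---|---|---|---|---|
| 0.5 | 10.07% | 6.39% | 7.55% | 1.16 |
| 1.0 | 11.82% | 5.57% | 7.95% | 2.38 |

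A hand check is possible at k = 1. Against the same POC, the SD of the difference is 0.09 × √(2 × 0.3) = 0.0697, and 0.798 × 0.0697 = 5.56%. Against an independent POC, it is √(2 × 0.05² + 0.0697²) = 0.0993, and 0.798 × 0.0993 = 7.92%. Both agree with the simulation.

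The total fall from before entry to after is 10.07 − 6.39 = 3.68 and 11.82 − 5.57 = 6.25 points. The artefact is 1.16/3.68 = 0.32 and 2.38/6.25 = 0.38 of that; the rest is genuine improvement.

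**Step 3: pooled artefact = s × f × q × artefact per pair.**

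- No delay: 0.25 × 0.5 × 0.5 × 1.16 = 0.07, and with 2.38, 0.15 points.
- 1 minute, 5-minute readings: q = 0.3 gives 0.04 to 0.09.
- 2 minutes, 5-minute readings: q = 0.1 gives 0.014 to 0.03.
- 2.5 minutes or more, 5-minute readings: 0.

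**Step 4: sensitivity, no delay.** Varying one input at a time: s = 0.05 gives 0.014 to 0.03 and s = 0.5 gives 0.14 to 0.30; ρ from 0 to 1 gives 0.05 to 0.35; meter error SD 3% to 7% gives 0.03 to 0.26. Combining s = 0.5, ρ = 1 and k = 1, the artefact per pair is 5.65, and 0.5 × 0.5 × 0.5 × 5.65 = 0.71.

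**Step 5: within calibrated devices, base case, no delay.** MARD is too low by 0.5 × 0.5 × 1.16 = 0.29 to 0.5 × 0.5 × 2.38 = 0.60 points. The width of the Bland-Altman limits (relative differences) is 45.0 against 46.1 percentage points at k = 0.5, and 52.3 against 54.2 at k = 1: about 2% to 4% narrower.

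**The case against.** The strongest reply is that everything beyond the shared meter is assumed. The calibration sentence is conditional: no passage says that a device needing calibration will enrol, how often it would be calibrated, how soon a value would be entered, or how far the next reading would move. Without that movement there is no artefact. The no-delay figures are the upper bound on timing when clocks agree. For scale, if patient-level MARD had an SD of 3 to 7 points (an assumption), the standard error with 150 patients would be 3/√150 = 0.24 to 7/√150 = 0.57, larger than the base-case artefact. All of this stands, and it is why the point is minor. It does not remove the point: the error has a known direction, does not shrink as patients are added, and is cheap to avoid.

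Three stronger readings are tempting and not supported.

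- A reader might infer that every calibration pair is circular. Pairs whose CGM reading precedes the entry are sound.
- A reader might count the whole fall in MARD after an entry as bias. A crude product of a 10% MARD, all pairs from calibrated devices, half of checks entered, q = 0.5 and full pull gives 10 × 1 × 0.5 × 0.5 × 1 = 2.5 points, but that includes genuine recalibration.
- A reader might conclude that the trial's accuracy verdict would be wrong. The plan gives no MARD criterion, so no verdict can be shown to flip.

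The opposite shortcut, that the effect is known to be small, is not established either; the 0.71 corner shows why.

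**Conclusion.** The point holds as a minor one. The plan lets one POC value act as both calibrator and reference for some devices, and the pairing rule does not exclude the pairs where this matters. The direction is towards better apparent accuracy. The documents do not fix the size: zero is possible, 0.07 to 0.15 pooled MARD points is the base illustration with no delay, and about 0.7 is an unfavourable combination of assumed inputs. These figures depend on the assumed device mix, calibration frequency, device response, noise correlation and meter error, and on entry delay and clock alignment. No stated decision is shown to change.

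**What to change.** In the Data Analysis Plan:

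1. Flag POC values entered as calibrations, with entry time, where the CGM download or an existing note shows them.
2. Leave out of the primary MARD, the range-specific MARDs and the Bland-Altman analysis any flagged pair whose CGM reading follows the entry. Keep the closest-reading rule for all other pairs.
3. Report one sensitivity analysis omitting all flagged pairs, and report MARD by calibration status.
4. Where entries cannot be identified, keep the planned pairing and report the result with and without those devices.
5. State two limitations: meter error carried into later readings is not removed, and leaving out post-entry pairs also sets aside some genuine improvement from recalibration.

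**Cost.** One paragraph and a little data handling; the documents do not say that the download shows entries. In the base case the pairs lost are s × f × q of all pairs: 0.25 × 0.5 × 0.5 = 6.25% at no delay, and 1.25% at 2 minutes with 5-minute readings (q = 0.1).

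The second limitation is not trivial. The model's MARD at non-calibration checks is 9.67% (k = 0.5) and 11.69% (k = 1). Within calibrated devices at no delay, MARD as planned is 0.5 × 9.67 + 0.25 × 10.07 + 0.25 × 6.39 = 8.95%. After the exclusion it is (0.5 × 9.67 + 0.25 × 10.07)/0.75 = 9.80%, a rise of 0.85 points of which 0.29 is artefact. At k = 1 the same sums give 10.19% and 11.73%, a rise of 1.54 points of which about 0.60 is artefact. Because of this, also show the closest-reading result without the exclusion. How patients calibrate does not change.
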